### Number Criteria

View 1	Already eat all their food within a window that is 10 h or shorter most (6/7) days of the week
View 2	Be underweight, as defined as a body mass index $\leq 18.5 \text{ kg/m}^2$
View 3	Have surgery planned during the study duration
View 4	Have any contraindications to the proposed nutrition intervention as identified by their medical provider, their designee, or the study team (e.g., type 1 diabetes, risk for hypoglycemia, medication requirements, pregnancy, breastfeeding, recent history of an eating disorder)
View 5	Be taking insulin
View 6	Be on enteral or parenteral nutrition

After entering the inclusion and exclusion criteria above, click the Save link. CICERO will automatically generate a printable Eligibility Checklist for you to use in your research. To review the checklist, click on the resulting link below. This checklist is also available under the Documents tab of this application.

 [Eligibility Checklist for HP-00099067\\_2 v1-23-2023-1674502822585\(0.01\)](#)

ID: VIEW4E0E5185F9000  
 Name: v2\_Eligibility

## Recruitment

1 \* Describe plans for recruitment, including the identification of potential participants (or acquisition of charts/records/samples) and initial interactions with them: (If this study involves the VA please list all sites at which recruitment will take place.):

1) Identification

Before recruitment, approval will be obtained by UMGCCC Clinical Research Center (CRC), the University of Maryland School of Nursing (UMSON), and the UMB Institutional Review Board (IRB). The study team will recruit participants using UMSON Department of Pain and Translational Symptom Science established procedures. Potential participants will be identified using three methods: a) screening medical records, b) direct referral from providers (e.g., nurses, nurse navigators, physicians), c) flyers, and (d) advertising via standard UMB- and ICTR-networks (e.g., the Elm).

a) Identification via medical records

Potentially eligible participants receiving care at UMGCCC will be identified in a HIPAA-compliant manner by study personnel via review of scheduled outpatient appointments (via EPIC) with [name], an oncologists on the study team. If other clinician(s) would like to participate in our study, we will add them to the study team and obtain permission to access their clinic schedule(s). Medical records typically show time since completion of adjuvant therapy (e.g., surgery, chemotherapy). If an individual appears to be eligible, the study team will contact the oncologist (or a designee) to notify them of a potential candidate and obtain approval to speak with/contact the patient.

b) Identification via direct referral from clinicians (e.g., physicians, physician assistants, nurses)

The study team is working with several oncologists (including, but not limited to [name]) and their medical teams (e.g., nurses, physician assistants) to identify potential patients at UMGCCC who are likely eligible for our study. If the patient is eligible based on information in the medical records, the provider will be asked to refer the person to the study team, tell the person about the study at their appointment (in person or telehealth), or give them a flyer. The medical team is not expected to field detailed questions related to the study.

c) Flyers

Flyers advertising our study will be placed in locations designated for such use. Potential participants can contact a member of the study team directly via phone or email for more information. Their medical provider will be contacted to ensure that the study is appropriate for the potential participant before consenting them.

d) Email advertising

We will advertise our trial via email through the UMB Office of Communications and Public Affairs's Elm Weekly and ICTR's relationship with ResearchMatch. As with flyers, potential participants can contact a member of the study team directly for more information. Their medical provider will be contacted to ensure that the intervention is appropriate for the potential participant before consenting them.

2) Recruitment

a) If the provider gives the study team permission to contact the participant, we will mail them a recruitment letter and/or send them a message via myPortfolio briefly introducing the study and asking them to contact us for more information.

b) If the provider introduced the study to the participant and has gotten permission for us to contact them, we will either meet them at/after their oncology appointment, send them an email, or call them.

After a potential participant has shown an initial interest in the study, we will review eligibility and discuss the study activities. If the person volunteers to participate, study personnel can obtain informed consent then or at a later date. After consent is provided, the participant will be provided with study materials.

3) Screening

For convenience to the potential participant, the person's clinic appointment might be combined with their screening and/or consent, or participants can undergo the screening and/or consent process remotely via phone and eConsent. To protect the privacy of potential participants, face-to-face recruitment discussions will be conducted in a private location.

A member of the study team will meet the potential participant in person or talk to them over the phone to explain the project and invite them to participate. It is expected that some patients will decline to participate, and some will not be eligible; approaching the same individual twice will be avoided by keeping a screening log containing the following information:

- Screening ID (1, 2, 3,...)
- Name
- Date of contact
- Medical record number
- How the participant learned of the study (e.g., our team, provider, flyer)
- Where/how we talked to the potential participant (e.g., clinic location, phone)
- Whether the patient was eligible or not
- If ineligible, the reason they are ineligible
- Whether the patient ultimately consented or declined
- If declined consent, the reason for declining consent
- If consented, the participant ID in the study (e.g., FRE01, FRE02, FRE03, ...)

Patients will need medical clearance from their provider to participate in the study.

Attached files:

Recruitment-letter.docx: For people whom we have gotten permission to contact from the oncology care team

telephone-script.docx: For people who have provided permission for us to contact them

telephone-script-2.docx: For people who call us for more information

2 \* Describe measures that will be implemented to avoid participant coercion or undue influence (if not applicable to the study, enter "N/A"):

To minimize coercion, the study team will emphasize that participation is completely voluntary and their cancer care will not be affected by their participation in the study.

3 \* Who will recruit participants (or acquire charts/records/samples) for this study? (Check all that apply)

- PI
- Study Staff
- Third Party

3.1 If you are using a third party, specify Third Party Recruiters:

4 Upload any recruitment tools such as screening/telephone scripts and introductory letters (do not upload advertisements here):

Name	Created	Modified Date
Recruitment-letter.docx(0.03)	2/22/2022 11:24 AM	3/11/2022 11:42 AM
telephone-script-2.docx(0.01)	3/10/2022 5:07 PM	3/10/2022 5:07 PM
telephone-script.docx(0.02)	2/22/2022 11:24 AM	3/10/2022 5:07 PM

**Advertising**

1 \* Will you be using advertisements to recruit potential participants?

Yes  No

ID: V1EW4E0BCCF811000  
Name: v2\_Advertising

## Advertising Detail

You indicated that you will be using advertisements to recruit potential participants.

1.1 \* Select the mode(s) of advertising (check all that apply):

- Radio
- Internet
- Print
- Television
- Other

1.1.1 If Other, specify:

Email: Elm Weekly, ResearchMatch  
MyPortfolio

1.2 \* Provide exact text of all proposed advertisement(s):

Cancer survivors: Did your treatment-related fatigue just never go away? Join a research study at University of Maryland, Baltimore, that aims to understand how diet, physical activity, and sleep patterns contribute to persistent fatigue.

Who is eligible?

- Cancer survivors who finished chemotherapy, radiation, and/or surgery 2 months-2 years ago
- People who are experiencing at least moderate fatigue on a regular basis
- People who tend to eat in a window greater than 10 hours on most days (e.g., breakfast at 8 a.m. and dinner at 7 p.m., a window of 11 hours)

What do I have to do?

- Participate in a 12-week study that collects data on food intake, physical activity, sleep patterns, sugar metabolism, and your symptoms, with a focus on fatigue.
- Provide feedback on a smartphone app that monitors food intake, physical activity, and sleep patterns for one week at the beginning, middle, and end of the study.
- Fill out questionnaires related to your eating patterns, fatigue, and other symptoms at the beginning, middle, and end of the study.
- Wear a physical activity monitor (e.g., FitBit) and glucose monitor for one week at the beginning, middle, and end of the study.
- Some participants will be asked to eat all their food within a self-selected 10-hour window during the day (e.g., 9am-7pm).

Do I get paid to participate?

Yes, Up to \$75.

Can I participate remotely?

Yes, all research activities can be done at home.

Please contact the study chair, [name], for more information.

[contact]

1.3 \* Upload advertisement(s) here:

Name

 SON-FREDA-Study-PC-v5.pdf(0.02)

Created

2/22/2022 11:28 AM

Modified Date

3/11/2022 11:44 AM

ID: VIEW4E0BCE82B8C00  
Name: v2\_Advertising Detail

## Research Related Risks

**If you uploaded a separate research protocol document in the 'Research Protocol' page, cite the applicable section and page numbers from that document in the answer box below.**

1 \* Individually list each research-related risk, using a separate line for each. Next to each risk, delineate the likelihood/seriousness of the risk, and the provisions for minimizing the risk:

a) Weight loss due to the intervention

Some studies have documented weight loss upon adoption of a TRE dietary pattern (10 hours of feeding/14 hours of fasting) despite consuming calories ad libitum. This intervention diet will be ad libitum and participants will be encouraged to satisfy thirst and hunger. However, due to the time-restrictive nature of the TRE diet compared to the typical American eating patterns, there is a chance that patients could enter a calorie deficit and lose weight during the course of the intervention. Minor weight loss will not be considered an adverse event (less than 3% in one week or 5% body weight every two weeks). However, if a patient experiences rapid, unintentional weight loss, the participant will be encouraged to contact the study team, medical monitor, and/or their treating oncology team. The CTCAE, version 5, will be used to report weight loss as an adverse event:

- Weight loss of 5% to less than 10% from baseline with no intervention indicated will be considered a Grade 1 adverse event.

- Weight loss of 10% to less than 20% from baseline and indicated nutritional support will be considered a Grade 2 adverse event.

- Weight loss greater than or equal to 20% from baseline with indicated tube feeding or total parenteral nutrition (TPN) will be considered a Grade 3 adverse event.

Weight loss can cause anxiety in cancer survivors who might think that their cancer is recurring. However, knowing that this dietary intervention often results in weight loss, particularly in people who are overweight, can be reassuring in that weight loss is due to dietary change and not a manifestation of progressive cancer, particularly if there are no other concerning symptoms.

As always, the patient has the right to eat or drink outside of the 10-h window, and to withdraw from the study at any time.

Likelihood: Moderate probability that some weight loss will be experienced, especially in patients with excess body fat; very low probability that a dangerous amount of weight will be lost

Seriousness: Low

Provisions for minimizing risk: In order to closely monitor weight change, each participant will be provided with a scale to use at home. It is likely that some participants will have personal goals to lose excess body fat—we will explain that this is not a weight loss study. In the event that rapid, unintentional weight loss occurs, the treatment team's recommendations for nutritional interventions due to any weight loss will be followed.

b) Hunger and hunger-related symptoms due to the intervention

Eating within a 10-h window will mean re-adjusting participants' typical eating patterns. Many participants will need to rearrange their meal times—either delay breakfast, eat dinner earlier, and/or forgo after-dinner snacks. If they delay breakfast, they might feel hungry in the few hours leading up to their eating window, especially in the first few days of the study. Similarly, they might crave something before bed if they are in the habit of eating before bed. With hunger can come lack of concentration, fatigue, dizziness, irritability, and other symptoms.

Likelihood: Moderate-high

Severity: Low to moderate

Provisions for minimizing risk: All participants will be encouraged to stay hydrated and to consume a snack outside of the window if symptoms become debilitating.

c) Emotional distress due to the intervention or the outcome measures

There is a chance that participants could become emotionally distressed by the expectation to consume food only in the 10-h window.

Likelihood: Low

Severity: Low

Provisions for minimizing risk: Each participant will be reassured that deviations from the plan are permitted, especially if they are feeling sluggish, dizzy, or sick, or if they are on a short trip/vacation.

d) Breach of confidentiality

There is always a risk of a breach of confidentiality in which sensitive medical information (e.g., medical history, AIDS status) could become known to persons outside the research team.

Likelihood: Very low

Severity: Low to high

Provisions for minimizing risk: To avoid leakage of sensitive information, only [name] (the study chair), coordinator(s), and any individual designees will have access to the screening log and the file that links participant name with participant number (both will be encrypted); these files will be stored on password-protected computers in the Department of Pain and Translational Symptom Science in the School of Nursing. All data files will reference participants by a non-identifiable Participant ID and will be stored on secure servers at UMB. All paper consent forms will be stored in a locked cabinet in [name] or the coordinator's office. If [name] shares data with any other researcher for analyses, all data will be deidentified (i.e., void of name, birthdate, and contact information). Presentation of data in the form of posters, presentations, grant applications, and manuscripts, either in private or public settings, will not have any identifiable information. [name] and all members of the study team participate in ethical training in accordance with University of Maryland policies (e.g., online coursework via the CITI collaborative).

e) Hypoglycemia due to fasting

The pancreas, via secretion of insulin and glucagon, maintains a constant blood sugar concentration of about 4-6 mM. After a meal, the pancreas will secrete insulin to promote the uptake of glucose into cells and, in response to falling glucose concentration a few hours later, the pancreas will secrete glucagon to promote gluconeogenesis, or the production/release of glucose in/from the liver and other tissues. This is a normal metabolic routine that occurs daily, especially during sleep (typically about 8 hours with no food). Fasting for prolonged periods of time can lead to hypoglycemia for a small percentage of individuals who have metabolic disorders and glucose dysregulation.

Likelihood: Low

Severity: Low to high

Provisions for minimizing risk: We are excluding participants who have type 1 diabetes, risk for hypoglycemia, or any other contraindications as determined by their provider. People who have type 1 diabetes or are at risk for hypoglycemia tend to know, and know that they should not fast for 14 hours overnight. In the consent form, we describe symptoms that are associated with hypoglycemia. We underlined that we encourage them to eat outside their eating window if they feel sluggish, dizzy, or sick. We will emphasize this while we go over the consent form with them and before they sign it. In the event that hypoglycemia occurs or is expected based on the participant's symptoms, the PI will meet with the participant to discuss the events surrounding the hypoglycemic episode and then meet with [name], the study doctor, to determine the course of action, which might include extending the eating window or having the participant stop the study.

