For the duration of the 12-week study, all participants may engage with the myCircadianClock app (see below) as much or as little as they like—with user input the app monitors eating, exercise, sleep patterns, and other measures. Also, the app will deliver weekly health tips and provide reminders about study activities (e.g., "Remember to weigh yourself today!"). To ensure that weight loss does not occur at an unhealthy rate, we will be providing participants with a bathroom scale for weekly measurements. Approximately every two weeks, the participant will receive a call from a study team member to check in; ask about symptoms and gauge use of the myCircadianClock app; ask about eating, sleeping, and exercise patterns; and for those in the TRE group, discuss adherence to the TRE pattern including barriers and how to overcome any barriers (See Engagement Script). During week 6 (midpoint), participants will be asked to complete questionnaires, log their sleep and eating habits using the app, wear the actigraph, and wear a continuous glucose monitor. During the last week of the study, week 12, participants will again be asked to complete questionnaires, log sleep and eating habits using the app, wear the actigraph, and wear a continuous glucose monitor. After completion of the study, participants will be asked to participate in a semi-structured interview during which we will solicit feedback on the study—what they liked about it, what they did not like about it, if they would recommend it to friends, etc. This will last approximately 15-30 minutes and will be audio-recorded with specific permission. Participants will receive \$25 at each time point if they complete at least 3/4 of the baseline, week 6, and week 12 study activities (5+ days of logging food intake, questionnaires, actigraphy, and continuous glucose monitoring) for a total of \$75; we will emphasize the importance of the food logs and questionnaires to answer our primary research questions. After completion of the study, those in both groups will have continued use of the myCircadianClock app.

myCircadianClock application ("app").

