#### Body weight

We will provide participants with a bathroom scale. Participants will be asked to place the scale on a level, hard surface (e.g., tile, wood), and weigh themselves in the morning shortly after waking with minimal clothing. Weekly body weight will be recorded in the myCircadianClock app.

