## Sample Size and Data Analysis

If you uploaded a separate research protocol document in the 'Research Protocol' page, cite the applicable section and page numbers from that document in the answer boxes below.

1 \* Provide the rationale and sample size calculations for the proposed target population:

This is a two-arm pilot randomized controlled trial that will assess the feasibility of recruitment and retention to a 12-week TRE trial facilitated by the myCircadianClock app as well as the preliminary efficacy of TRE vs. a control arm on the treatment of cancer-related fatigue.

It is common that single-arm pilot studies implementing dietary interventions recruit 10-40 participants (e.g., TRE study among overweight older adults, n=10; ketogenic diet among patients with recurrent glioblastoma, n=20; lifestyle intervention including diet among overweight breast cancer survivors, n=14). In total, 30 participants will be recruited, and approximately 10-20% attrition is anticipated, providing evaluable data from approximately 25 participants. We had more dropouts than anticipated and are upping our sample size to 50 participants so that we can have about 25 participants with evaluable data.

2 \* Provide the plan for data analysis. Include in the description the types of comparisons that are planned (e.g., comparison of means, comparison of proportions, regressions, analysis of variance, etc.), which is the primary comparison/analysis, and how the analyses proposed will relate to the primary purposes of the study:

We will conduct an interim analysis of feasibility after 10 participants have been enrolled. If any unanticipated barriers arise in regard to feasibility of recruitment, data collection, and/or retention, logistical changes will be made to the protocol as appropriate.

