## Prospective Data

You indicated that the study involves the collection of prospective data.

1 \* Where is the data being collected from? (Check all that apply)

- Medical records
- Medical images
- Commercial (for profit) entity
- Publicly available records
- Schools
- Other

1.1 If Other, please specify:

myCircadianClock app, questionnaires, researcher-provided glucose monitor and actigraph, interview, adverse events

2 \* What data fields will you have access to/collect for the study? For example, name, initials, date of birth, Social Security number, income, demographic information, family units, housing, etc.

The Clinical Record form will be completed by study staff from the medical record. The Clinical Record form contains demographics, height, weight, current menopausal status, Karnofsky Performance Status or Eastern Cooperative Oncology Group (ECOG) Performance Status, comorbidities, cancer stage, surgical procedures, types and doses of treatments (e.g., chemotherapy type and dosing, hormone therapy), most recent blood work (e.g., hemoglobin, hematocrit, lymphocytes, etc.), and medical history (e.g., prior myocardial infarction).

myCircadianClock app: diet, sleep, exercise, and health data (We will have access to all that the participant inputs.)

Questionnaires: Please see section 5, Surveys/Questionnaires

Glucose monitor: Interstitial glucose data

Actigraph: Movement data (counts in three axes) and data from the light sensor

Adverse events: patient-reported worsening of symptoms, with special attention to weight loss and severe adverse events (e.g., hospitalization) as defined by the CTCAE v 5.0. Please see section 12, Study Monitoring.

You can also upload a copy of the data fields/variables to be collected for the study:

Name	Created	Modified Date
 Clinical-record.docx(0.01)	2/22/2022 11:32 AM	2/22/2022 11:32 AM

ID: VIEW4E0E25B643800

Name: v2\_Prospective Data

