**3.1 If Yes, when?**

**4 \* Briefly describe the DSM review process itself. Will it be an open or closed review to the investigator? Blinded/unblinded data? How will confidentiality of individual participant data be maintained?**

The UMGCCC DSM/QAC will provide independent monitoring. The below items are considered in DSM/QAC annual review. The semi-annual review will include only those items below related to safety.

- A cover form (Annual Renewal DSM/QAC) completed by the study team summarizing the activities of the prior reporting period.
- All severe adverse events (SAEs) and protocol-designated expeditiously reportable adverse events (AEs), internal and external, including those that have previously been reported to the DSM/QAC. The DSM/QAC will have a full report on all internal SAEs concerning that clinical trial, including the nature of the SAE, grade, therapeutic agents involved, whether they were reported to all appropriate agencies within the mandated timeframes, and the investigator's assessment of whether the toxicity was study-related. The DSM/QAC may recommend to the CRC to close studies with adverse event profiles that deviate in a substantial way from expected patterns of events.
- The consent form to determine if modifications are needed based on the accumulated AEs and SAE information.
- A summary of protocol deviations that have not yet been reviewed by the DSM/QAC.
- If available, interim outcomes and other results are assessed to see if response rates conform to estimates used to develop the statistical analysis. The DSM/QAC may recommend study closure to the CRC for studies with poorer than expected response rates that cannot meet stated outcomes targets even if the trial accrued fully. Conversely, response rates significantly greater than expected may lead to early termination of trials to prevent further assignment of patients to the inferior treatment arms in comparative trials.
- Periodic audit results, if available. The DSM/QAC may recommend study closure to the CRC for studies when the PI or research team show a pattern of persistent non-compliance with Good Clinical Practices policies.

Upon conclusion of review, the DSM/QAC decides one of the following:

- Award final DSM/QAC approval to the protocol
- Find that minor revisions are needed for final DSMB approval
- Find that major corrections are needed to the protocol
- Suspend immediately to prevent harm to subjects or others

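### The rate-based exemption for weight loss contradicts the plan's own Grade 1 rule: a steady loss of about 0.43% to 2.53% per week is exempt under one and an adverse event under the other

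*Combined protocol and SAP*

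**What the plan says.** Research Related Risks, item 1(a), contains both rules.

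- The exemption, by speed: "Minor weight loss will not be considered an adverse event (less than 3% in one week or 5% body weight every two weeks").
- The reporting standard: "The CTCAE, version 5, will be used to report weight loss as an adverse event".
- The first grade, by total change: "Weight loss of 5% to less than 10% from baseline with no intervention indicated will be considered a Grade 1 adverse event". Grade 2 starts at 10% and also requires that nutritional support be indicated. Grade 3 starts at 20% and also requires that tube feeding or parenteral nutrition be indicated.

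Three other places bear on the point.

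- Prospective Data, item 2, describes adverse events as patient-reported worsening of symptoms, "with special attention to weight loss and severe adverse events (e.g., hospitalization) as defined by the CTCAE v 5.0".
- Study Procedures gives the reason for the scale: "To ensure that weight loss does not occur at an unhealthy rate, we will be providing participants with a bathroom scale for weekly measurements". Under Body weight it adds: "Weekly body weight will be recorded in the myCircadianClock app".
- Monitoring Plan – Internal DSMB, item 4, lists among the matters reviewed: "The consent form to determine if modifications are needed based on the accumulated AEs and SAE information".

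None of these says which rule takes precedence, or that the exemption ends once the total loss reaches 5%.

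**The concern.** The two rules measure different things. One looks at the change over one or two weeks and starts afresh each fortnight. The other looks at the change since baseline. A participant who loses weight slowly throughout the intervention can satisfy both, so the same loss is declared not to be an adverse event and also declared to be Grade 1. Two staff members could record it differently and each be following the plan.

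Weight loss is the first risk listed, and the plan gives some loss a moderate probability. Gradual loss is also the pattern that a speed test is least able to detect. What is at stake is consistent classification of that risk, including in the accumulated adverse events that the monitoring committee considers when it decides whether the consent form needs changing.

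**Working it through.** The plan gives no figure on this point to reproduce. The check asks which steady rates of loss satisfy both rules.

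**Inputs, all from the plan**

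- Speed limits: under 3% in one week, under 5% in two weeks (Research Related Risks, item 1(a)).
- Grade 1 band: at least 5% and under 10% from baseline (same item).
- Duration: 12 weeks of intervention (Study Procedures, item 3).
- Weighing: weekly (Body weight).

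**Model.** Loss at a constant proportion r per week, so the total loss after k weeks is 1 − (1 − r)^k.

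**Lower end.** The loss must reach 5% by week 12: (1 − r)^12 = 0.95, so r = 1 − 0.95^(1/12) = 0.427% per week.

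**Upper end.** The two-week loss must stay under 5%: (1 − r)^2 = 0.95, so r = 1 − 0.95^(1/2) = 2.532% per week. This is also under 3% in one week, so the two-week limit is the binding one.

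**Examples**

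| Loss per week | Two-week loss | First weekly weight at 5% or more | Loss at that week | Loss at week 12 |
|---|---|---|---|---|
| 0.43% | 0.86% | week 12 | 5.04% | 5.04% |
| 0.5% | 1.00% | week 11 | 5.36% | 5.84% |
| 1.0% | 1.99% | week 6 | 5.85% | 11.36% |
| 2.0% | 3.96% | week 3 | 5.88% | 21.53% |
| 2.53% | 4.996% | week 3 | 7.40% | 26.47% |

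**Does every such rate pass through Grade 1?** Yes. At the last weighing before the 5% line is crossed, the weight is above 95% of baseline. One more week removes at most 2.532% of it, so the loss at the first crossing is at most 1 − 0.95 × 0.97468 = 7.41%. That is inside the Grade 1 band.

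**Sensitivity**

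- Loss linear in baseline weight: 5/12 = 0.42% to just under 2.5% per week.
- Horizon of 11 or 13 weeks: the lower end becomes 0.47% or 0.39%.
- Meeting either speed limit is enough for the exemption: the upper end rises to just under 3%.

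The overlap stays wide in every case.

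**The case against.** The strongest reply is that the item can be read coherently. It exempts only minor loss, gives short-interval figures as an illustration of it, and then names CTCAE version 5 as the reporting standard with bands from baseline. Prospective Data names the same standard. On that reading the one- and two-week figures screen out fluctuation, and any loss of 5% from baseline is graded. The sentence about an unhealthy rate explains why participants weigh themselves; it does not define an adverse event.

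Most of this stands: the baseline grades are the likelier intention. But the exemption is categorical, its two-week limit renews without a cumulative cap, and the plan's described response to weight loss is framed around fast, unintended loss. Staff could reasonably treat speed as the gate and CTCAE as the scale for what passes it.

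The upper part of the range is also not a forecast. A loss of 26.5% in 12 weeks is far beyond the 2.6% that the plan cites from a 12-week study of an 8-hour window in obese adults, and the item itself rates a dangerous loss as very unlikely.

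A reader might infer more than the documents support:

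- **That gradual losses would vanish from the data.** Weights are to be logged weekly and a baseline weight is taken, so the grade percentages can be recomputed where weights exist, although no section plans to do so. What is uncertain is the adverse event label.
- **That Grades 2 and 3 are exempted in the same way.** They also require indicated nutritional support, or tube feeding or parenteral nutrition. The 11.36% in the table is therefore not automatically a graded event.
- **That reporting will be biased by arm.** The trial is open label, so this is possible, but nothing shows it, and Sample Size and Data Analysis plans no comparison of adverse events between arms.
- **That monitoring is seriously weakened.** The committee's full case reports cover severe events. Grade 1 weight loss enters mainly through the consent form item, for a risk that the plan already lists first.

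**Conclusion.** The inconsistency is real and minor. As written, a steady loss of about 0.43% to 2.53% per week over 12 weeks is not an adverse event under the exemption and is Grade 1 under the grading rule. The certain conflict is at Grade 1 only. The feasibility, fatigue and mechanistic results are unaffected.

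The range rests on a constant percentage loss, a 12-week horizon and both speed limits being met. Real weights fluctuate, and a gradual loser may cross a weekly limit by chance, in which case the exemption no longer applies. The documents give no 12-week distribution of weight change in cancer survivors, so no number of affected participants is offered.

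**What to change.** In Research Related Risks, item 1(a), state one rule: a loss of 5% or more from the week 0 weight, in either arm and at any speed, is an adverse event graded by the plan's CTCAE bands, with a note of whether the loss was intended. Reword the 3%-in-one-week and 5%-in-two-weeks figures as triggers for contacting the participant, not as an exemption.

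This changes wording only and uses weights that are already being collected. The downside is a few more Grade 1 entries, some of them for intended loss, which is why intent should be noted.
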